Gait and balance disturbances in MS are already common even in the early stages of the disease. Half of the patients refer some alteration in the quality of their gait within the first month after diagnosis, reaching 90% at 10 years of evolution.⁴ ⁵ Furthermore, gait is the most valuable body function for MS patients, both for those with less than 5 years of evolution and for those with more than 15 years, as walking restriction hardly affects their activity and participation level.⁷

Gait disturbance is caused by multiple factors such as decreased muscle strength, balance, coordination, and proprioception, impaired vision, spasticity, fatigue and even cognitive impairment.⁴

Some impairments arise in the physical and social context of each patient, limiting participation in activities or therapies to improve balance, fatigue, strength and gait characteristics such as fatigue, high risk of falls or high disability.⁷

This would support the development and application of rehabilitation strategies for mitigating the energetic penalties of gait abnormalities during ambulation. Some of these interventions include aerobic, resistance, yoga, and combined exercise training, that have shown significant improvements in walking endurance regardless of outcome measures (6MWT, 2MWT).⁸

New emerging approaches might involve Robot-assisted gait training. In the last 5 years a lot of robotic solutions that offer both strategies of support in daily living and rehabilitative devices have appeared. Some studies have shown that people with multiple sclerosis and severe gait impairment who participated in Robot-assisted gait training (RAGT) achieved significant improvement in lower limb muscle strength and increased their walking speed, although the effect was not long-lasting.⁹

In the last years evidence about robot-based rehabilitation for PwMS has been published, and currently, more than 5 devices have been approved for its use in gait neurorehabilitation. Yeh et al. concluded that Robotic locomotor training limitedly affects motor functions of multiple sclerosis, but improves fatigue and spasticity, it is safe and well-tolerated for PwMS and less demanding for physical therapists.¹⁰ Bowman et al. concluded that Robotic-Assisted Gait therapy (RAGT) improves balance and gait out-

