3.2.2 Exclusion criteria

- Pregnancy.
- Starting or switching from fampridine (Fampyra®) in the last 4 weeks.
- Height and weight outside the secure standard of safe use, described in the safety guides.
- Contraindications for Atalante training (eg, bone instability, history of osteoporosis or osteoporotic fractures).
- Subjects under Corticosteroids treatment or relapse.
- Changes in disease-modifying and symptomatic therapy for MS during the study period.
- Subjects with psychiatric or cognitive comorbidities that may interfere with the trial.
- Whose joint centers cannot be aligned Atalante's.
- Ranges of motion below:
 - Knee: 5° extension, 110° flexion

- Ankle: 0° dorsiflexion, 9° plantar flexion, 18° inversion and eversion
- Hip: 115° flexion, 15° extension, 17° abduction, 10° adduction, 10° medial rotation, 20° lateral rotation
- Severe spasticity (greater than Ashworth 3) or uncontrolled clonus.
- Severe concurrent medical diseases: infections, circulatory, heart or lung, pressure sores.
- Active implantable medical device.

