3.4 Assessments

The following information will be collected for all patients: age, sex, weight, height, type of MS, years from the diagnosis, Expanded Disability Status Scale (EDSS) and type of support device.

To ensure that training sessions are well tolerated, we will assess patients' blood pressure and heart rate weekly. We will also monitor the appearance of pain in any part of the body related to the RAGT at end of each training session using a pain registry (type of pain, location, intensity)²⁷.

3.4.1.1 To reduce the incidence of any type of muscle injury the physical therapist before each RAGT session will assess the level of spasticity using the Numeric Rating Scale measure of spasticity (NRS). The 0–10 NRS asks patients to indicate their level of spasticity on a scale of 0–10, where 0 is no spasticity and 10 is the worst possible spasticity. This type of rating tool is widely utilized in clinical settings to quickly assess pain.²⁸

A record of any unexpected Serious Adverse Events (SAE) within trial episodes will be kept. These are defined as death, a life-threatening adverse event or an event occurring as a result of the use of the device that requires medical intervention.

After the 8 weeks of rehabilitation treatment (T2) and, if possible, one year after T4, peripheral blood (6ml) will be taken from all subjects to perform the subsequent molecular analysis.

Molecular analysis

Peripheral blood mononuclear cells (PBMCs) will be purified using the Ficoll-Hypaque density gradient method according to manufacturer's instructions. Briefly, whole blood will be extracted by venepuncture and collected in CPT Vacutainer tubes (Becton Dickinson, BDAM362781) and centrifuged at 2250g for 25 min. Supernatant will then be collected, and washed twice with enriched saline (0.9% NaCl, 2%FBS). PMBC containing pellet will then be resuspended with 1 ml of complete media (RPMI1640 + 2% FBS) and cells will be counted and assessed for viability using a Countess 3 automated cell counter (Invitrogen). PBMCs will be adjusted to 5×10^6 cells/ml in freezing media media (90% FBS, 10% DMSO), and frozen at -80°C using a [name]™ Freezing Container (Thermo Scientific™) for 24 h and stored in liquid nitrogen vapor phase.

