3.4.2 Schedule

Following completion of day 1 assessments and randomization, all subjects will be scheduled for the intervention phase of the study. Each participant will receive 24 sessions of RAGT or cRHB scheduled for three times a week for 8 weeks. If a subject cancels a treatment session, it will be counted as missed session. If a subject misses three consecutive treatment sessions, they will be dropped from the study due to inconsistency in treatment carryover. Cancellations and changes in patient scheduling represent a true clinical environment and represents normal clinical patient management.

At the end of the intervention phase, a new exploration will be carried out.

[figure not shown]

Figure 1 schedule

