Descriptive statistics (i.e., mean, standard deviation) will be calculated for quantitative data (demographics and clinical characteristics and outcome measures). Frequencies will be calculated for qualitative variables. For the proportions, binomial proportion confidences will be calculated using the Wilson formulae. Proportions will be compared using the Newcombe formulae

The Wilcoxon bilateral matched-pairs test will be used to compare repeated measurement on a single sample (mean, standard deviation).

Study data were collected and managed using REDCap electronic data capture tools hosted at the Mayo Clinic. REDCap (Research Electronic Data Capture) is a secure, web-based application designed to data capture for research studies, providing: 1) an intuitive interface for validated data entry; 2) audit trails for tracking data manipulation and export procedures; 3) automated export procedures for seamless data downloads to common statistical packages; and 4) procedures for importing data from external sources (Harris et al., 2009).

5 References

6. Larocca NG. Impact of Walking Impairment in Multiple Sclerosis Perspectives of Patients and Care Partners Conclusions: Difficulty walking is a common impairment in people with MS, with adverse effects on the QOL of people with MS and care partners of a person with MS. *Patient.* 2011;4(3):189-201.

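### Randomised participants who miss three sessions in a row leave the study, and the plan states no follow-up, analysis set or missing-data method for them

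*Combined protocol and SAP*

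**What the plan says.** Section 3.4.2 puts the rule in the treatment period: "Following completion of day 1 assessments and randomization, all subjects will be scheduled for the intervention phase of the study". It then says that "If a subject cancels a treatment session, it will be counted as missed session" and that "If a subject misses three consecutive treatment sessions, they will be dropped from the study due to inconsistency in treatment carryover". The rule ends participation in the study, not only in training, and the reason given concerns treatment.

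The assessment table schedules the 10-metre walk, the primary outcome, at baseline (T1), end of training (T2) and two months later (T3). Neither the table nor 3.4.2 says whether a dropped participant attends T2 or T3.

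Section 4 contains a sample-size statement, descriptive statistics, interval methods for proportions, and two comparison methods: "Proportions will be compared using the Newcombe formulae" and "The Wilcoxon bilateral matched-pairs test will be used to compare repeated measurement on a single sample". It names no analysis population, missing-outcome method, sensitivity analysis or dropout allowance.

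**The concern.** The primary aim is a randomised comparison of RAGT with cRHB on walking speed, with 30 per arm. The drop rule selects participants by what they do after allocation. If those removed differ between arms in number or in prognosis, a comparison of those who remain is no longer protected by randomisation.

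The protocol gives grounds for expecting attendance to relate to prognosis. Its introduction describes impairments "limiting participation in activities or therapies to improve balance, fatigue, strength and gait characteristics such as fatigue, high risk of falls or high disability". Section 3.4 adds, for the exoskeleton, "We will also monitor the appearance of pain in any part of the body related to the RAGT at end of each training session", so the investigators regard device-related pain as possible. That makes a link between arm and missed sessions plausible but does not demonstrate one.

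The planned methods do not close the gap. The comparison of proportions has no defined denominator: a dropped participant could be left out, counted as a non-responder or imputed, and the choice could be made after the data are seen. The matched-pairs test uses only participants with both values, so anyone without T2 contributes nothing.

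A separate point needs clarification. Section 3.2.2 lists as an exclusion criterion "Changes in disease-modifying and symptomatic therapy for MS during the study period". This can be observed only after enrolment, and no consequence is stated. It might be a second route of removal after randomisation.

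**Working it through.** **Inputs from the protocol.** 24 sessions, three a week for 8 weeks (3.1, 3.4.2); removal after three consecutive misses (3.4.2); 30 per arm (3.1). The plan gives no figure for missed sessions or dropout, so there is none to reproduce. Its stated size of 15 patients (section 4) comes without a null or comparator rate, so it cannot be re-derived, and this point does not depend on it. All rates below are assumptions.

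**1. How often the rule would apply.** Let *p* be the chance of missing any one session, independently, and *a(n)* the probability of no run of three misses in *n* sessions. Then *a(0) = a(1) = a(2) = 1* and

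*a(n) = (1−p)·a(n−1) + p(1−p)·a(n−2) + p²(1−p)·a(n−3)*.

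The chance of meeting the rule is *1 − a(24)*:

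| Assumed *p* | Meets rule | Expected of 60 |
|---|---|---|
| 5% | 0.3% | 0.2 |
| 10% | 2.0% | 1.2 |
| 15% | 6.2% | 3.7 |
| 20% | 13.5% | 8.1 |
| 25% | 23.8% | 14.3 |

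Absences often cluster (illness, travel). If each week instead carries a chance *q* of whole-week absence, the probability over 8 weeks is *1 − (1−q)⁸*:

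- *q* = 1%: 7.7%, about 5 of 60
- *q* = 2%: 14.9%, about 9 of 60
- *q* = 3%: 21.6%, about 13 of 60

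**2. What the remaining participants leave undetermined.** Suppose *k* of 30 are dropped in each arm and the completers respond equally at 50%. For *k* = 4, completers are 13/26 in each arm. If all four dropped in one arm are responders and all four in the other are not, the all-randomised rates are 17/30 and 13/30, a difference of 4/30 = 13.3 points. In general the range is ±*k*/30: ±6.7, ±13.3 and ±20.0 points for *k* = 2, 4 and 6. The completers' counts cancel, so the width does not depend on the 50%, only on equal completer rates and equal numbers dropped.

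**3. Direction.** Take a true response of 50% in both arms, a fraction *d* = 20% dropped from one arm and none from the other, with the dropped responding at rate *r*. That arm's completer rate shifts by *(0.5 − d·r)/(1 − d) − 0.5*:

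- *r* = 20%: (0.5 − 0.04)/0.8 − 0.5 = +7.5 points
- *r* = 50%: (0.5 − 0.10)/0.8 − 0.5 = 0
- *r* = 80%: (0.5 − 0.16)/0.8 − 0.5 = −7.5 points

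The bias can go either way, and it vanishes when the dropped resemble the retained.

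**4. Precision.** The confidence interval widens by √(30/*n*): √(30/27) = 1.054 (about 5%) at 27 per arm, and √(30/24) = 1.118 (about 12%) at 24 per arm.

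**The case against.** The strongest reply is that the harm is inferred. The protocol does not say that T2 and T3 are withheld from dropped participants or that their data are excluded, and the schedule figure in 3.4.2 is not available to us. That is correct. What is certain is the rule and the silence around it; a completers-only analysis is the natural reading, not a stated one. A schedule figure is also an unlikely place for an analysis set or missing-data method, and the statistical section is available and has neither.

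Second, the link to arm is thin. The introduction speaks of therapies in general and also cites a systematic review finding robotic training safe and well tolerated, and a pain registry does not show that pain leads to cancellations. This stands: a relation to outcome is plausible from the text, while a difference between arms is only possible.

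Third, the Wilcoxon test is described for a single sample, so pairs lost there do not themselves bias the comparison between arms. This also stands; the undefined denominator for the proportions is what bears on that comparison.

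Fourth, every magnitude is assumed. At independent miss rates of 5% to 10% the rule affects about 0 to 1 of 60. The 7.5-point shift needs 20% dropped from one arm only, and it is roughly half the standard error of the difference: √(0.25/24 + 0.25/30) = 13.7 points. The illustrations therefore do not show that bias would be decisive. The case for changing the plan rests on the outcomes being unrecoverable and the remedy cheap.

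**Conclusion.** The concern holds and must be fixed before participants are dropped. Confidence is high that a post-randomisation removal rule exists and that the plan states no all-randomised set, no follow-up of those removed and no missing-data method. The size and direction of any bias cannot be derived from the documents. Under the assumed miss patterns, anything from almost nobody to about 14 of 60 would be removed. With 2 to 6 dropped per arm and equal completer response, the data would leave the all-randomised difference undetermined within ±6.7 to ±20 points. If removals are equal in both arms and unrelated to outcome, the cost is precision alone, but the plan offers no means of checking that. Whether three missed sessions should end training is a clinical matter and is not judged here.

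**What to change.** - **Section 3.4.2.** Separate stopping training from leaving the study. Whatever is decided about continuing training, say that missed sessions do not end participation and that T2 and T3 assessments are still sought.
- **Section 4, analysis set.** Define the primary comparison as all randomised participants in their allocated arm.
- **Section 4, missing outcomes.** State the method in advance. Options are a likelihood-based repeated-measures model of walking speed, or multiple imputation of speed before deriving the 20% response, with a sensitivity analysis for outcomes not missing at random. Other methods could serve; the need is to fix one before the data are seen.
- **Reporting.** Give the number dropped and the reasons by arm. An analysis of adherent participants can be kept as a labelled sensitivity analysis.
- **Section 3.2.2.** Ask the sponsor whether the therapy-change item is an entry criterion or a post-randomisation event. If the latter, record it and keep the participant in follow-up and in the primary analysis.

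The cost is protocol and analysis wording, plus T2 and T3 visits for about 1 to 14 participants under assumed independent miss rates of 10% to 25%. Some will still decline to attend, so the missing-data method is needed in any case. Including non-adherent participants may dilute the estimated effect.

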3.5 Device

3.5.1 Description

Atalante is the first exoskeleton designed and developed by Wandercraft. Atalante is intended to perform ambulatory functions, mobility exercises and adapted physical exercises, hands-free for individuals having lower limb and trunk disability in rehabilitation centers, city cabinets or adapted physical exercise centers under the supervision of a trained operator.

The device is available with one unique model and allows for length mechanical adjustment of specific parts so that patients with different physical characteristics can undergo care sessions with the same unit of Atalante - after it has been adjusted to their own set of measurements.

Figure 2 shows the main parts of the device.

Figure 2: Atalante main parts

Atalante is an exoskeleton composed of:

- **Two operated legs** made up of articulated parts: thigh, leg, and foot. These parts can move thanks to 12 actuators comprised each of an electric motor, a position sensor (encoder), and a motor controller board to process related data. Figure 3 shows the location of each of the actuators. In addition, the thighs and legs are adjustable in length to allow adaptation to different patient morphologies. The lower structure is made of aluminium alloy, parts of which are covered by plastic shells.
- **A back**, made of composite material, which links the lower limbs together and supports the upper body of the patient.
- **A vest**, made of fabric, and equipped with an inertial sensor (IMU) to detect the intention of the patient inside the exoskeleton based on the motion of his chest. The vest is available in two sizes: small (S) and large (L).
- **Five additional inertial sensors** located in the back, legs and feet for orientation estimation of different parts of the exoskeleton.
- **Force sensors** placed in the feet for contact state estimation.
- **An embedded computing system** (Wanderbrain and Wanderneuron software) to retrieve data from all sensors and boards, and coordinate motion - determining commands for the actuator blocks.
- **A set of plastic wedges** to adapt to the patient morphology. The wedges compensate for a less than 16° dorsal flexion of the ankle and/or increase the distance between the patient's knee and Atalante's foot. They exist in 8 different sizes in terms of inclination (between 0 and 16°) and height and they are placed on Atalante's feet, if needed.
- **A battery system** consisting of two pluggable and rechargeable packs of Lithium-Ion cells enclosed in plastic casings and located each on the thighs.

[figure not shown]

Figure 3: Atalante joints

The ranges of motion of the 12 joints are constrained by mechanical stops and supplemented by software stops to protect the patient's joints from exceeding motion limits. Atalante is attached to the patient in 3 locations per leg (thigh, leg, foot) plus at the abdomen level thanks to the vest's belt. These interfaces are made of rigid shells covered with foams and equipped with adjustable straps that maintain the patient and facilitate transmission of the system movements to the patient, all while ensuring their comfort. The rigid shells are located at the back of the patient's thigh and at the front of the leg.

Atalante is controlled (Figure 4) by its user thanks to:

- Sensors, especially a motion sensor (i.e., the IMU) placed on the back of the vest which triggers the movement.
- Two keyboards, one for the operator (physio controller) leading the care session and one remote intended for either the operator or optionally the patient.

[figure not shown]

Figure 4: Control interface of Atalante

As Atalante is destined to be used in healthcare facilities, city cabinets or adapted physical exercise centers with several patients in a day, the angular amplitudes of each articulation have been designed to allow a broad range of patients to be included into the exoskeleton.

Furthermore, the device is equipped with mechanical adjustments allowing the length of the legs and the thighs to be regulated in the range 40-49 cm and 38-46 cm respectively, according to the dimensional measurements of the patients. The angular amplitudes of the 12 motorized articulations and the mechanical adjustment ranges are shown in the figure below.

[figure not shown]

Figure 5: Angular amplitudes and mechanical adjustments of the V5 exoskeleton

Atalante exoskeleton is part of a system (Figure 6) composed of:

- **DataGen**: a dynamic adaptation of the algorithms is performed by a computation software running on a server called DataGen. It takes as input the patient measurements and computes a model of Atalante and the patient, as well as patient-specific trajectories for standing, sitting, walking, repositioning, and turning. All these outputs are transmitted to the exoskeleton.
- **AGUI (commercial name WanderTouch)**: an application running on a portable device, called AGUI, offers a way to communicate with the exoskeleton using Bluetooth communication, as well as with DataGen using Wi-Fi. Data flows from AGUI to DataGen (patient measurements) and back from DataGen to AGUI to Atalante exoskeleton (algorithm outputs). AGUI also allows for real-time configuration and monitoring of a session, by fine tuning the gait pattern, and by selecting the level of assistance (ActiveGait) provided by Atalante to the patient while performing walking steps. Gait can be resistive (ActiveGait up to -25%), fully supported by the patient (ActiveGait 0%), assisted by Atalante at a chosen level per leg (ActiveGait up to 100%), or fully passive where Atalante provides all the necessary effort to perform the gait. Additional indicators are collected and available on AGUI per session and per patient.
- **Bluetooth dongle**: plugged in the back of Atalante and used to establish the communication between the AGUI and the exoskeleton.
- **Battery charger** for the removable battery packs that power the exoskeleton.
- **Dynamometric screwdriver** to adjust the thighs and legs.

[figure not shown]

Figure 6: Atalante system

In addition, the Atalante system is used in combination with

- a seat with the following characteristics:
 - o A minimal depth of 40 cm,
 - o A minimal width of 65 cm,
 - o A height in the range 40-55 cm,
 - o Able to support at least 200 kg,
 - o Be covered with a cushion.
- an electrical safety rail having the following characteristics:
 - o Legally marketed medical device intended to support or lift people (compliance with ISO 10535 "Hoists for the Transfer of Disabled Persons - Requirements and Test Methods" standard or equivalent).
 - o Stable and installed in accordance with the manufacturer instructions.
 - o Able to support at least 200 kg.

The electrical safety rail and the seat are not distributed by Wandercraft. Only the swivel to link the safety rail to Atalante is provided with its protection. An example of safety rail without the protection is shown in Figure 6 below.

[figure not shown]

Figure 7: Atalante fixation to a safety rail without the protection

The exoskeleton is handled by the remote control, the "operator" interface located on the right-hand side of Atalante's back and the sensor and an installation button located on Atalante's thighs at knee level at each side. The patient or the healthcare or the adapted physical activity professional select a mode or transition by pressing the relevant button. Then, the patient moves the bust; the sensor placed on the patient's back detects the patient's intention and trigger the movement.

The various modes and transitions are listed below:

- SITTING position: stable and comfortable sitting position.
- STANDING position: stable and comfortable standing position. The STANDING button also allows to switch to "exercise" mode, to stand up and to stop the motion.
- SITTING DOWN transition allows the patient to switch from standing up to sitting down.
- WALKING mode allows the patient to walk with Atalante.
- ROTATION mode allows the patient to turn with Atalante to the left or right.

- REPOSITION mode allows the patient to perform side and back steps with Atalante.
- INSTALLATION mode allows the patient to be transferred from his/her wheelchair to Atalante, or vice versa.

